5. GENERAL STATISTICAL METHODS

5.1. Determination of Sample Size

The planned enrollment for this study is 300 patients. For the change from baseline at Month 12 in the 6-MWT, assuming a treatment difference of 33 meters between patisiran and placebo in the treatment-naïve group and 20 meters in patients with baseline tafamidis, the weighted average treatment difference between patisiran and placebo in the overall population is approximately 29 meters (standard deviation [SD] = 75 meters), assuming 70% are in the treatment-naïve group and 30% are in the baseline tafamidis group. A sample size of 300 patients provides >90% power for a 2-sided test to detect a mean difference between treatment arms at a 2-sided alpha = 0.05.

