5.6. Visit Windows

Scheduled visits are expected to follow the protocol schedule. All data will be tabulated and analyzed per the evaluation visit as recorded on the electronic case report form (eCRF) even if the assessment is outside of the visit window.

For 6-MWT and KCCQ, assessments will be conducted at baseline and at Months 6, 9, and 12 in the 12m-DB period and at Months 18, 21, 24, 30, 33, 36, 42 and 48 in the OLE period. For all longitudinal efficacy assessments, if a scheduled post-baseline assessment is not performed, assessments performed within ± 1.5 months of the scheduled assessment will be grouped with the scheduled assessments for that timepoint for analysis, with the following exception:

- For patients randomized to placebo who received patisiran in the OLE period, assessments performed after the first OLE dose will not be grouped with the scheduled Month 12 visits even if they are within ± 1.5 months.

The derived visits will be used for all analyses.

Unless otherwise specified above, data collected at unscheduled visits will be included in by-patient data listings and figures but no assignment to a study visit will be made for the purpose of by-visit summary tabulations. However, unscheduled visits may be used in the calculation of baseline values (as discussed in Section 5.4) and for inclusion in any categorical shift summaries (eg, shift from baseline to “worst” post-baseline value).

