 - b. Patisiran patients who have missing data while on treatment: Patients are expected to continue to show benefit from treatment similar to that observed at the scheduled time point. Therefore, missing data during the on-treatment period (within 60 days of their last dose) are considered MAR and will be imputed using MI estimated from all non-missing data collected on treatment from the patisiran arm.
 - c. Patisiran patients who have missing data after stopping their study treatment: Patients will no longer benefit from treatment in the future and will have trajectory similar to placebo patients after discontinuing treatment. Therefore, missing data after treatment discontinuation (more than 60 days after last dose of study drug) will be imputed using the data from placebo patients using the copy reference (CR) approach.
3. Patients who die during the 12m-DB period (not due to COVID-19) or who have become unable to walk due to progression of ATTR amyloidosis by Month 12 and have missing data: Assuming that deaths observed in the study will likely be related to worsening of disease, the missing Month 12 6-MWT change from baseline will be imputed as the worst 10th percentile change, capped by the worst possible change for the patient (ie, 0 – baseline 6-MWT). The imputation will be done for patients from both the patisiran and placebo arms.

Missing values will be imputed 100 times to generate 100 complete datasets using the procedures described above. The stratified Wilcoxon Rank Sum test (stratified by baseline tafamidis use) will be applied to each imputed dataset for the change from baseline in 6-MWT at Month 12. The Z scores estimated from the stratified Wilcoxon Rank Sum test fit to each imputed dataset will be combined by applying Rubin's rules, [Rubin 1996; Rubin 1987] using SAS PROC MIANALYZE to produce inferential results for the p value.

The effect size comparing treatment groups will be estimated using the stratified HL estimate (stratified by baseline tafamidis use) of the median difference in the change from baseline between patisiran and placebo, together with its 95% CI. The calculation will be repeated for each imputed dataset, and the results will be combined by applying Rubin's rules, [Rubin 1996;

[Rubin 1987](#)] using SAS PROC MIANALYZE to obtain the stratified HL estimate and corresponding 95% CI.

More details on the implementation of the control-based imputation for missing data are discussed in Appendix [9.1](#).

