For patients who are alive through the 12m-DB period and who have not become unable to walk due to progression of ATTR amyloidosis, all missing data for the placebo arm and missing data for the patisiran arm during the on-treatment period (ie, assessments within 60 days of the last dose of study drug) will be imputed using MI under the MAR assumption. Since the pattern of missing data within patients may be non-monotone, multiple imputation will be conducted separately by treatment arm and baseline tafamidis use group using the Markov Chain Monte Carlo (MCMC) method. For each treatment arm/baseline tafamidis use group, the imputation model will include type of amyloidosis (hATTR vs. wtATTR), NYHA class (I/II vs. III), age at randomization (<75 vs. ≥75), NT-proBNP (≤3000 ng/L vs >3000 ng/L), baseline 6-MWT, and

all calculated values of change from baseline in 6-MWT at pre-specified visits. The input dataset DATAIN will exclude data from patients in pattern 5 above and exclude data from patisiran patients that were collected after treatment discontinuation (ie, more than 60 days after the last dose of study drug). Below is a sample SAS code for the multiple imputation:

```
proc mi data=DATAIN out=DATA_STEP1 seed=234 nimpute=100;
  by treatment bltaf;
  em maxiter=300 converge=1e-4 itprint outem=outem;
  var baseline_variables 6MWT_base 6MWT_chg_m6 6MWT_chg_m9 6MWT_chg_m12;
  mcmc chain=multiple initial=em;
run;
```

The MI procedure generates imputed values for all missing values. For patisiran patients, the imputed data from the on-treatment period will be kept while the imputed data after treatment discontinuation will be discarded and replaced by either the observed non-missing values (if available) or the imputed values using the CR approach described below. The imputation model will include type of amyloidosis (hATTR vs. wtATTR), NYHA class (I/II vs. III), age at randomization (<75 vs. ≥75), NT-proBNP (≤3000 ng/L vs >3000 ng/L), baseline 6-MWT, and all calculated values of change from baseline in 6-MWT at pre-specified visits.

```
proc mi data=DATA_STEP1_2 out=DATA_STEP2 nimpute=1 seed=xxx;
  by _imputation_ bltaf;
  class treatment;
  fcs nbiter=30 reg (6MWT_chg_m12 = baseline_variables 6MWT_base
    6MWT_chg_m6 6MWT_chg_m9);
  mnar model (6MWT_chg_m12 / modelobs=(treatment='placebo'));
  var baseline_variables 6MWT_base 6MWT_chg_m6 6MWT_chg_m9 6MWT_chg_m12;
run;
```

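### The Appendix 9.1 step-2 sample code restricts only Month 12 to placebo, so it does not carry out the stated copy-reference rule for off-treatment Month 6 and 9 values; the resulting error can go in either direction

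*SAP*

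**What the plan says.** All references are to the main SAP, Amendment 2.1.

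- **Assumption.** Section 6.6.1.3, Sensitivity Analysis 2, item 2c: "Patients will no longer benefit from treatment in the future and will have trajectory similar to placebo patients after discontinuing treatment".
- **Rule.** The same item: "missing data after treatment discontinuation (more than 60 days after last dose of study drug) will be imputed using the data from placebo patients", by copy reference. Pattern 4 in Appendix 9.1 repeats this, within each baseline tafamidis group.
- **What happens to step-1 values.** Appendix 9.1, for patisiran patients: "the imputed data after treatment discontinuation will be discarded and replaced by either the observed non-missing values (if available) or the imputed values" from copy reference. The sentence is not limited to Month 12. Section 5.6 gives three post-baseline visits in this period: "assessments will be conducted at baseline and at Months 6, 9, and 12 in the 12m-DB period".
- **Code.** Step 1 runs by treatment and baseline tafamidis. Step 2 runs by imputation number and baseline tafamidis, reads a dataset called DATA_STEP1_2, uses FCS with 30 iterations, and lists the Month 6, 9 and 12 changes in the VAR statement. Treatment is a CLASS variable but is not in VAR. The only placebo restriction is "mnar model (6MWT_chg_m12 / modelobs=(treatment='placebo".

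**The concern.** A patisiran patient who stops early and leaves has Month 6 and/or Month 9 missing again once the step-1 imputations are discarded. The text calls for copy reference at those visits. The code gives them no placebo restriction, no separation by arm and no treatment term, so by default they come from a regression fitted to both arms together. They are then predictors in the placebo-only Month 12 regression. The Month 12 value is therefore not the copy-reference value that the text describes.

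Sensitivity Analysis 2 is the only control-based imputation of the primary rank test: Sensitivity Analysis 1 keeps the missing-at-random imputation and Sensitivity Analysis 3 is a missing-at-random MMRM. Its purpose is to show what happens if patients who stopped patisiran gain nothing further. A programmer working from the prose and one working from the code would report different results for it.

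**Working it through.** **Anchor.** Section 5.1 plans for a Month 12 difference of about 29 m with an SD of 75 m, and claims: "A sample size of 300 patients provides >90% power for a 2-sided test". The significance level is 0.05. This reproduces:

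- Weighted effect: 0.7 × 33 + 0.3 × 20 = 29.1 m.
- Standard error with 150 per arm: 75 × √(2/150) = 8.66 m.
- Power: Φ(29/8.66 − 1.96) = Φ(1.39) = 0.918.

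**Assumptions, not in the SAP.** The benefits at Months 6 and 9 and the correlations between visits. The placebo mean change is set to 0, since only differences matter.

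**Models implied by the code.** Let d be the vector of benefits and S the within-arm covariance. If affected patients are few, the pooled arms have mean d/2 and covariance S + dd′/4. Months 6 and 9 are regressed on the other visits with these pooled moments. Month 12 is regressed on Months 6 and 9 with placebo moments (mean 0, covariance S). FCS cycles through the three regressions 30 times. True copy reference uses placebo moments throughout: its expected Month 12 value is 0 if all three visits are missing, and the Month 6 to Month 12 slope times the observed Month 6 value if only Month 6 is observed.

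**One case in full:** d = (10, 20, 29), SD 75, equal correlation 0.7, all three visits missing.

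- Within-arm variance 5625, covariance 0.7 × 5625 = 3937.5.
- Pooled means 5, 10, 14.5. Pooled variances 5650, 5725, 5835.25. Pooled covariances 3987.5 (Months 6 and 9), 4010 (6 and 12), 4082.5 (9 and 12).
- Month 6 = −4.905 + 0.412 × Month 9 + 0.399 × Month 12.
- Month 9 = 1.883 + 0.408 × Month 6 + 0.419 × Month 12.
- Month 12 = (0.7/1.7) × (Month 6 + Month 9) = 0.412 × (Month 6 + Month 9).
- These three equations settle at Month 6 = −8.3, Month 9 = −3.6, Month 12 = −4.9 m.

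True copy reference gives 0, so the code is 4.9 m harsher on patisiran here. The pooled regressions expect a Month 12 change of 14.5 m on average. A placebo-like Month 12 draw falls below that, and when the benefit grows over time it pulls Month 6 below the placebo level.

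**Departure from true copy reference at Month 12 (m per affected patient):**

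| Benefit at Months 6/9/12 | Visits missing | Correlation 0.5 | 0.7 | 0.85 |
|---|---|---|---|---|
| 10/20/29, equal correlation | 6, 9, 12 | +0.2 | −4.9 | −18.4 |
| 10/20/29, equal correlation | 9, 12 | +1.3 | +0.9 | +0.6 |
| 10/20/29, AR(1) | 6, 9, 12 | +1.8 | −0.2 | −6.7 |
| 5/15/29, equal correlation | 6, 9, 12 | −2.2 | −9.4 | −27.4 |
| 29/29/29, equal correlation | 6, 9, 12 | +7.1 | +8.3 | +9.0 |
| 29/29/29, AR(1) | 6, 9, 12 | +4.7 | +5.8 | +6.6 |

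A Monte Carlo emulation of the first row gave +0.1, −4.9 and −18.7.

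**Arm level.** If 10% of the patisiran arm were affected, all with three visits missing, the shift in the arm mean would be 0.10 × 9.0 = +0.9 m to 0.10 × (−18.4) = −1.8 m, and 0.10 × (−27.4) = −2.7 m for the slowest trajectory. At 5% these halve. The share is an assumption. The analysis itself is a rank test, so a shift in means is only a guide.

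**The case against.** **A reader might infer that the code always leaves part of the treatment benefit in, and so flatters patisiran.** Feeding pooled Month 6 and 9 means of 5 and 10 m once into the placebo regression suggests this: 0.412 × (5 + 10) = +6.2 m at correlation 0.7. That is not the coded algorithm. FCS also re-imputes Months 6 and 9 given the imputed Month 12, and with the same inputs the result after 30 cycles is −4.9 m. A wider set of 36 scenarios gave a positive departure in 32, but two of its three trajectories already had at least 20 m of benefit by Month 6. That count reflects the trajectories chosen, and the SAP gives no Month 6 or 9 effects to choose by.

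**The code is only a sample.** It is labelled so and contains placeholders, and the prose rule is clear. This lowers the importance. It does not settle which version a programmer will follow.

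**The stated assumptions concern Month 12.** Section 6.6.1.3 and the pattern list in Appendix 9.1 are framed that way, and Month 12 does get a placebo model. That stands. But the discard-and-replace sentence in Appendix 9.1 covers every off-treatment visit, and the Month 12 model uses those visits as predictors.

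**DATA_STEP1_2 is undefined.** It might hold only placebo and pattern-4 patients, which would remove most of the pooling. The SAP does not say so. Even then, observed on-treatment values of pattern-4 patients would enter the unrestricted Month 6 and 9 regressions.

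**KCCQ-OS.** Section 6.6.2.1.3 imports the assumptions of Section 6.6.1.3, not this code. Its pattern mixture model is affected only if the code is reused.

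**Conclusion.** The mismatch between text and code is real and no other section corrects it. Run as written, step 2 does not deliver the stated copy reference for patisiran patients who have a missing off-treatment Month 6 or 9 value together with a missing Month 12 value. Patients with those visits observed, or who stopped later, are unaffected. Benefit carried forward through an observed on-treatment value is part of copy reference and is not an error.

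Neither the size nor the sign of the departure can be fixed from the SAP. It is negative and sometimes large when all three visits are missing, benefit builds up gradually and visits are strongly correlated. It is positive when most of the benefit is present by Month 6. It is about 1 m in the 10/20/29 scenarios when Month 6 is observed. The documents do not support a claim of systematic bias towards patisiran.

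Even with 10% of the arm affected, the main scenarios shift the arm mean by −1.8 to +0.9 m, or at most 1.8/8.66 = 0.21 of the planning standard error. The point is confined to Sensitivity Analysis 2; the primary analysis does not use this step. All of this assumes the default PROC MI treatment of a listed continuous variable without its own model: regression on the other VAR variables, using all observations in the BY group. It deserves correction because the sensitivity analysis should do what it says and the correction is nearly free.

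**What to change.** - Extend the restriction to every visit that can be re-imputed: `mnar model (6MWT_chg_m6 6MWT_chg_m9 6MWT_chg_m12 / modelobs=(treatment='placebo'))`, with matching FCS regression models for Months 6 and 9.
- Define DATA_STEP1_2: which patients it holds, and which values are set back to missing. Limiting it to placebo and pattern-4 patients is not a full substitute for the MODELOBS restriction.
- If the code is reused for the KCCQ-OS pattern mixture model, state that the same specification applies.

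The cost is one changed code line with its matching models, and a sentence or two in Appendix 9.1. It needs no new data and changes neither the estimand nor the primary analysis.

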9.2. Calculation of Stratified Win Ratio *p* value and Confidence Interval

Dong et al (2018) [Dong 2018] note that the logarithm of the stratified win ratio is asymptotically normally distributed with mean $v_{\log(WR)}$ and variance $\sigma_{\log(WR)}^2$, with these terms defined in equations 7b and 8 in their paper, respectively. The point estimate of the mean, $\hat{v}_{\log(WR)}$, is the logarithm of the stratified win ratio statistic defined in Section 6.6.2.2. The variance estimate, $\hat{\sigma}_{\log(WR)}^2$, is calculated under the null hypothesis of the same treatment effect in the patisiran and placebo groups.

Then $\hat{z} = \frac{\hat{v}_{\log(WR)}}{\sqrt{\hat{\sigma}_{\log(WR)}^2}}$ is a standard normal deviate from which the *p* value is readily obtained.

The 95% confidence interval for the logarithm of the stratified win ratio is constructed as

$$\hat{v}_{\log(WR)} \pm 1.96 * \sqrt{\hat{\sigma}_{\log(WR)}^2}$$

and the limits of this confidence interval will then be exponentiated to construct the 95% confidence interval for the stratified win ratio.

9.3. Questionnaire/Scoring

In questionnaires, if multiple responses are provided to a single-response question, the question is deemed as missing.

9.3.1. Kansas City Cardiomyopathy Questionnaire (KCCQ)

The Kansas City Cardiomyopathy Questionnaire is a 23-item self-administered questionnaire developed to independently measure the patient's perception of their health status, which includes heart failure symptoms, impact on physical and social limitation, and how their heart failure impacts their quality of life within a 2-week recall period.

There are 10 summary scores for the KCCQ tool, which are calculated as follows:

1. Physical Limitation

Code responses to each of Questions 1a-1f as follows:

- Extremely limited = 1
- Quite a bit limited = 2
- Moderately limited = 3
- Slightly limited = 4
- Not at all limited = 5
- Limited for other reasons or did not do the activity = <missing value>

If at least 3 of Questions 1a-1f are not missing, then compute

- Physical limitation score = $[(\text{mean of the non-missing Questions 1a-1f}) - 1] / 4 * 100$

2. Symptom Stability

Code the response to Question 2 as follows:

- Much worse = 1
- Slightly worse = 2
- Not changed = 3
- Slightly better = 4
- Much better = 5
- I've had no symptoms over the last 2 weeks = 3

The symptom stability score = $[(\text{Question 2}) - 1] / 4 * 100$.

3. Symptom Frequency

Code responses to Questions 3, 5, 7 and 9 as follows:

- Questions 3 and 9
 - Every morning/night = 1

- 3 or more times a week but not every day = 2
- 1-2 times a week = 3
- Less than once a week = 4
- Never over the past 2 weeks = 5
- Questions 5 and 7
 - All of the time = 1
 - Several times a day = 2
 - At least once a day = 3
 - 3 or more times a week but not every day = 4
 - 1-2 times a week = 5
 - Less than once a week = 6
 - Never over the past 2 weeks = 7

If at least two of Questions 3, 5, 7 and 9 are not missing, then compute

- $S3 = [(Question\ 3) - 1]/4$
- $S5 = [(Question\ 5) - 1]/6$
- $S7 = [(Question\ 7) - 1]/6$
- $S9 = [(Question\ 9) - 1]/4$

The symptom frequency score = (mean of S3, S5, S7, S9)*100.

4. Symptom Burden

Code responses to Questions 4, 6 and 8 as follows:

- Extremely bothersome = 1
- Quite a bit bothersome = 2
- Moderately bothersome = 3
- Slightly bothersome = 4
- Not at all bothersome = 5
- I've had no swelling/fatigue/shortness of breath = 5

If at least one of Questions 4, 6 and 8 is not missing, then compute

- Symptom burden score = $[(\text{mean of the non-missing Questions 4, 6 and 8}) - 1]/4 * 100$

5. Total Symptom Score

Total symptom score = mean of the following available summary scores

- Symptom Frequency Score
- Symptom Burden Score

6. Self-efficacy

Code responses to Questions 10 and 11 as follows:

- Question 10
 - Not at all sure = 1
 - Not very sure = 2
 - Somewhat sure = 3
 - Mostly sure = 4
 - Completely sure = 5
- Question 11
 - Do not understand at all = 1
 - Do not understand very well = 2
 - Somewhat understand = 3
 - Mostly understand = 4
 - Completely understand = 5

If at least one of Questions 10 and 11 is not missing, then compute

- Self-efficacy score = $[(\text{mean of the non-missing Questions 10 and 11}) - 1] / 4 * 100$

7. Quality of Life

Code responses to Questions 12, 13 and 14 as follows:

- Question 12
 - It has extremely limited my enjoyment of life = 1
 - It has limited my enjoyment of life quite a bit = 2
 - It has moderately limited my enjoyment of life = 3
 - It has slightly limited my enjoyment of life = 4
 - It has not limited my enjoyment of life at all = 5
- Question 13
 - Not at all satisfied = 1
 - Mostly dissatisfied = 2
 - Somewhat satisfied = 3
 - Mostly satisfied = 4

- Completely satisfied = 5
- Question 14
 - I felt that way all of the time = 1
 - I felt that way most of the time = 2
 - I occasionally felt that way = 3
 - I rarely felt that way = 4
 - I never felt that way = 5

If at least one of Questions 12, 13 and 14 is not missing, then compute

- Quality of life score = $[(\text{mean of the non-missing Questions 12, 13 and 14}) - 1] / 4 * 100$

8. Social Limitation

Code responses to each of Questions 15a-15d as follows:

- Severely limited = 1
- Limited quite a bit = 2
- Moderately limited = 3
- Slightly limited = 4
- Did not limit at all = 5
- Does not apply or did not do for other reasons = <missing value>

If at least 2 of Questions 15a-15d are not missing, then compute

- Social limitation score = $[(\text{mean of the non-missing Questions 15a-15d}) - 1] / 4 * 100$

9. Overall Summary Score

Overall summary score = mean of the following available summary scores

- Physical Limitation Score
- Total Symptom Score
- Quality of Life Score
- Social Limitation Score

10. Clinical Summary Score

Clinical summary score = mean of the following available summary scores

- Physical Limitation Score
- Total Symptom Score

9.3.2. Norfolk Quality of Life-Diabetic Neuropathy (QOL-DN)

Norfolk QOL-DN is a tool for assessing patients' perception of the effects of diabetes and diabetic neuropathy. There are 35 questions divided into 5 domains. The range of possible total scores is -4 to 136.

Part I: Symptoms

Items 1-7 (Part I) are a simple inventory of symptoms of neuropathy. The presence of the symptom is checked in whichever box applies, and an absence of a symptom is checked under "none." Positive responses are scored as 1; and negative responses, as 0.

Part II: Activities of Daily Life

Items 8-35 (Part II) pertain to Activities of Daily Life, and most of these are scaled on a 5-point Likert scale ranging from 0 ("Not a problem") to 4 ("Severe problem"). However, Questions 31 and 32 are scored differently. In Question 31, "Good", the middle item, is scored as 0. "Very Good" is scored as -1, "Excellent" is scored as -2. "Fair" is scored as 1, and "Poor" is scored as 2. In Question 32, "About the Same," the middle item, is scored as 0. "Somewhat better" is scored as -1, "Much better" is scored as -2. "Somewhat worse" is scored as 1, and "Much worse" is scored as 2.

Subscales and Scoring Algorithm

The Total QOL and 5 domains should be summed as follows:

- Total QOL (35 items) $\Sigma(1-7, 8-35)$
- Physical Functioning/Large Fiber (15 items) $\Sigma(8, 11, 13-15, 24, 27-35)$
- Activities of Daily Living (ADLs) (5 items) $\Sigma(12, 22, 23, 25, 26)$
- Symptoms (8 items) $\Sigma(1-7, 9)$
- Small Fiber (4 items) $\Sigma(10, 16, 17, 18)$
- Autonomic (3 items) $\Sigma(19, 20, 21)$

Domain scores are calculated as the rounded integer value of the average scores of non-missing included items multiplied by the number of items if at least 50% of the items are non-missing. A domain score is missing if more than 50% of the included items are missing.

If the scores for all 5 domains are non-missing, then Total QOL is the sum of scores of the 5 domains; however, if at least 1 of the domains is missing and at least 50% of the items (18 items) are non-missing, then Total QOL is calculated as 35 times the mean of the non-missing items, rounded to the nearest integer. Otherwise, Total QOL is deemed as missing.

Signature Page for VV-CLIN-006731 v2.0
ALN-TTR02-011 SAP Amend2.1

Task: Approval Verdict: Approve	[Redacted] GMT+0000
------------------------------------	---------------------

Task: Approval Verdict: Approve	[Redacted] GMT+0000

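### Norfolk QoL-DN: the 0/1 rule for items 1-7, read per item, gives a total range of -4 to 115, which contradicts the stated -4 to 136

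*SAP*

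**What the plan says.** Section 3 names Appendix 9.3.2 as the place for the Norfolk QoL-DN scoring algorithm, so this appendix is the operative specification. It states:

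- "There are 35 questions divided into 5 domains", and "The range of possible total scores is -4 to 136".
- "Items 1-7 (Part I) are a simple inventory of symptoms of neuropathy". On how they are answered: "The presence of the symptom is checked in whichever box applies, and an absence of a symptom is checked under 'none". On how they are scored: "Positive responses are scored as 1; and negative responses, as 0".
- Items 8-35 mostly run from 0 to 4. "However, Questions 31 and 32 are scored differently": each runs from -2 to +2.
- The total is the sum of all 35 items. The Symptoms domain is items 1-7 plus item 9.
- A domain is missing if more than half of its items are missing. Otherwise it is the mean of the answered items times the number of items. If any domain is missing but at least 18 items are answered, "Total QOL is calculated as 35 times the mean of the non-missing items, rounded to the nearest integer".

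Section 9.3 adds a general rule for questionnaires: several responses to a single-response question make that question missing. Section 6.6.3 analyses the change in Total Score at Month 12 by ANCOVA and allows a repeat in patients with a history of neuropathy. The same scoring text stands in the original SAP and in Amendments 1 and 2.

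**The concern.** The scoring rule and the stated range in one section cannot both hold if each of items 1-7 is worth at most one point. The text mentions boxes but gives neither the number per item nor a rule for adding them, so a programmer could code each item 0/1 in good faith.

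If that happened, a patient who checks one box on an item and a patient who checks several would score alike, and the total could not be read against the printed range. The Section 9.3 rule adds a second risk. If items 1-7 are handled as single-response questions, an answer with more than one box checked becomes missing. That could remove the Symptoms domain and send the total to the fallback.

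**Working it through.** **Inputs** (all from Appendix 9.3.2): 7 Part I items; 28 Part II items, of which 26 run 0 to 4 and two (31 and 32) run -2 to +2. The five domain lists contain 15 + 5 + 8 + 4 + 3 = 35 items and cover items 1-35 exactly once, so no gap comes from a dropped item.

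**Attempt to reproduce the stated range.** With m the maximum score of one Part I item:

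- Minimum = 7×0 + 26×0 + 2×(-2) = **-4**. This agrees with the SAP.
- Maximum = 7m + 26×4 + 2×2 = 7m + 108.

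| m | Total maximum | Symptoms domain maximum (7m + 4) |
|---|---|---|
| 1 | 115 | 11 |
| 2 | 122 | 18 |
| 3 | 129 | 25 |
| 4 | **136** | 32 |

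Only m = 4 gives 136. Two other variants also fail: all of items 8-35 on 0 to 4 with Part I at 0/1 gives 112 + 7 = 119, and all 35 items on 0 to 4 gives 140.

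**Size of the gap.** 136 - 115 = 21 points (7 items × 3). The stated range spans 136 - (-4) = 140, so 21/140 = 15%.

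**Total fallback under 0/1 scoring** (35 × mean of answered items, worst answer on every answered item):

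- Items 1-7 missing: 35 × 108/28 = 135.
- Whole Symptoms domain missing (items 1-7 and 9): 35 × (25×4 + 2×2)/27 = 35 × 104/27 = 134.8.
- Either way the result is about 20 points above the attainable 115.

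**Same fallback if items 1-7 run 0 to 4.** With items 1-7 missing the result is again 135, now inside 136.

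**Prorating still leaves the range with items 1-7 at 0 to 4**, because items 31 and 32 have a different range from the rest:

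- Symptoms domain and items 31 and 32 missing, all else at 4: 35 × 100/25 = 140.
- Physical Functioning with only items 31 and 32 missing, the rest at 4: 15 × 4 = 60, against a complete-data maximum of 13×4 + 2×2 = 56. With the other domains at maximum the total is 60 + 20 + 32 + 16 + 12 = 140.
- Low end, 18 items answered and a domain missing, items 31 and 32 at -2 and the rest 0: 35 × (-4)/18 = -7.8, below -4.

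**Mid-scale case.** Take every Part I item at its maximum, the 26 items at 2, and items 31 and 32 at 1. Under 0/1 the complete total is 7 + 52 + 2 = 61, and with items 1-7 missing the fallback is 35 × 54/28 = 67.5. Under 0 to 4 the complete total is 28 + 52 + 2 = 82 against the same 67.5. A gap arises under both rules, so this case does not count against 0/1 scoring in particular.

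**The case against.** The strongest reply is that this is an ambiguity and not an arithmetic error. The scoring sentence speaks of responses, not items, and the text refers to boxes. One point per checked box is a fair reading, and with four boxes it gives exactly 136. The Section 9.3 rule is confined to single-response questions, which leaves room for items that accept several checks. The endpoint is also exploratory, Section 5.7 gives exploratory endpoints no multiplicity adjustment, and the 20-point overshoot needs most symptom items missing with the worst answer everywhere else.

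Much of this stands. The per-box reading is plausible, and the loss of points depends on how the score is programmed. The overshoot is a corner case. The reply does not remove the problem, however: the section states neither the number of boxes nor that they are summed, and it does not exempt items 1-7 from the multiple-response rule.

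Three stronger inferences are tempting and are not supported:

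- That the trial's totals have in fact lost 21 points. The SAP does not show which reading is programmed.
- That the boxes are body sites, so that spread of symptoms would go unseen. The SAP never says what the boxes represent.
- That 0/1 scoring is the only cause of out-of-range totals, so that correcting it restores the range everywhere. The 140 and -7.8 cases show otherwise.

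**Conclusion.** The contradiction is real. Under the per-item reading the range is -4 to 115, which cannot be reconciled with -4 to 136 in the same section. The documents alone do not prove which statement is wrong. That each of items 1-7 runs 0 to 4 is a well-supported inference: it is the only variant tried that gives 136, and it fits the mention of boxes.

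Conditional on per-item programming, the effect is 21 of 140 range points (15%), a Symptoms domain maximum of 11 instead of 32, and a fallback that can exceed the attainable maximum by about 20 points. Scoring at 0/1 enlarges the overshoot but is not its sole cause.

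The primary and secondary endpoints are unaffected. The point is still worth correcting before analysis, because the score enters an ANCOVA and the correction is cheap.

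**What to change.** After checking the instrument's scoring manual, add to Appendix 9.3.2:

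1. For items 1-7, each checked symptom box scores 1 and the item score is the sum of the checked boxes (0 to 4; none = 0). This item score is used in the Symptoms domain, in the total and in both missing-item rules.
2. The multiple-response rule in Section 9.3 does not apply to items 1-7.
3. The range -4 to 136 holds for complete questionnaires. Either cap prorated domain and total scores at their complete-data range, or note that prorating can give values outside it because items 31 and 32 run -2 to +2.

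If the manual instead supports 0/1 per item, correct the stated range to -4 to 115.

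The cost is two or three sentences and a programming check. No new data are needed, provided that the individual boxes are captured.
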